Dementia is the most expensive condition in the United States (US).⁽¹⁾ The high costs are driven in part by the prolonged course and intensity of the disease and heavy care demands on family members.⁽²⁾ A significant contributor to care demands are the behavioral and psychological symptoms of dementia (BPSD) (e.g., depression, irritability, agitation, anxiety) that the majority of persons with dementia (PwD) experience.⁽³⁾ These BPSD have been linked to care partner (CP) depression, burden, and grief,^(4, 5) and in turn, BPSD frequency increases when CPs are depressed and burdened.^(5, 6) De Vugt et al.⁽⁷⁾ found that CP reactivity to BPSD predicted skilled care placement, which is concerning

because skilled care makes up the largest portion of the average annual cost per person of US \$50,201.⁽⁸⁾ Despite evidence that BPSD contribute to care costs, the literature on the cost efficacy of Telehealth-based interventions for BPSD is limited. Further, while numerous technology-based interventions exist, little attention is given to implementation costs or to the potential cost savings of these interventions.

STELLA (Support via TEchnology: Living and Learning with Advancing ADRD) is an intervention designed to address the need for a personalized approach to teach CPs strategies in managing BPSD. This real-time educational intervention is designed for families caring for those in moderate to late-stages of dementia. STELLA uses videoconferencing to connect CPs, in their own homes, with experienced Guides. The Guides use cognitive behavioral techniques to assist CPs in identifying and implementing strategies to reduce distressing behavioral symptoms in the PwD. This in turn diminishes CP burden and depression.⁽⁹⁾ Our pilot work found that early versions of -STELLA reduced the frequency BPSD and CP reactivity to them.^(10, 11) The subjective and objective outcomes of STELLA are now being tested in the ORCASTRAIT Living Lab, with the goal of scaling STELLA up to address the needs of the 16 million CPs in the US. To prepare for effective future scaling of STELLA, the longer-term costs of implementing the intervention, as well as the cost benefits of the intervention need to be determined.

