As many as 90% of all US managed care organizations (MCOs) report using cost in determining coverage of treatments, drugs, and other interventions, while 40% specifically report the use of cost-effectiveness analyses.⁽¹²⁾ An increasing awareness of the fiscal challenges confronting the Medicare program and other public payors in the US suggest that interventions which improve outcomes and decrease costs will be well-received.⁽¹³⁾ Approval by both public and private payors is therefore a first step in wide dissemination of a new intervention in the US health system. The approval process begins with quantifying an intervention's cost as well as the intervention's cost-efficacy compared to other interventions. Thus, understanding the costs of STELLA will advance the program toward a pragmatic trial and ultimately toward widespread adoption in the US health system.

3. Project Description

Care Partners will participate in an 8-week intervention in which a Guide (e.g., nurse or social worker) will help them identify and modify distressing behavioral symptoms of dementia. We will measure Care Partner affective symptoms, including depression and burden, as well as quality of life for both the Care Partner and the person with dementia. Assessments will occur prior to, during, and after the intervention (Table 3).

This study is ancillary to an existing IRB-approved prospective longitudinal observational study which enables and accelerates the process of developing, translating and disseminating innovative Care Partner interventions facilitated by technology. The ORCASTRAIT study (IRB#20236) is currently enrolling 120 dyads (patients with dementia, and a family Care Partners). ORCASTRAIT uses sensors and other technologies in participants' home setting to monitor and detect (through novel algorithms) early changes in health, cognitive function, activity, and behavioral-functional signatures of patients and Care Partners. The proposed ancillary study will target informal Care Partners enrolled in ORCASTRAIT, and follow changes in their stress and health over the study period. This ancillary study will incorporate data from the parent study, will add the Care Partner (STELLA) intervention and measure Care Partner coping with an additional 5 surveys to the electronic (online) surveys that informal Care Partners are already completing over the parent study period.

4. Study Population

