a. Care Partners and Persons with Dementia. Up to 40 Care Partners and their 40 care-recipients with ADRD will participate in this study. The primary focus of this study is on Care Partners, however, we will gather subjective and objective data on participants with ADRD to assess the effect of the intervention on Care Partner affective responses to caregiving and quality of life for both. STELLA participants will be recruited from the existing cohort of patients, and their Care Partners, who are enrolled in the ORCASTRAIT Life Laboratory (OSLL).

There has been no pilot testing of STELLA with non-English speaking care partners, and all materials have been tested in English. Therefore, only English-speaking participants are included in STELLA.

b. Inclusion and exclusion criteria. The research team will assess eligibility of interested parties based on the criteria listed in Table 1. In the event of a screen failure, data collected during screening will be destroyed at the end of the study. The recruitment team will track the number of care partners contacted for the study, the number consented, the number of those that dropped out and the number of those that completed the entire intervention.

Table 1: Inclusion/Exclusion Criteria

Participant	Inclusion	Exclusion
Care Recipient	
 Diagnosis of ADRD, moderate to late stages Exhibits 2 or more behaviors listed on RMBPC¹⁶ that are bothersome to the Care Partner and occur 3 or more times/week at study enrollment Family member of Care Partner (this can be a relative, spouse or close kin that is considered family) 	
 Dementia not related to ADRD Unable to leave Care Partner during Partner training Early stage dementia, as defined by MoCA of about 15/30 or higher.

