Intervention (4 weekly sessions)	Meet with for 4 weekly sessions, beginning with Session 1 . (see Table 2)	After Mercury Baseline survey completed
Starlet Survey (Survey 2)	Electronic assessment of depression, burden	1 month after Session 1
Intervention (4 weekly sessions)	Meet with Guide and up to 4 other Care Partners for 4 more weekly sessions (See Table 2)	After session #8
Venus Survey (Survey 3)	Full assessment, including program survey	2 months after Session 1
Post-STELLA Assessment	Complete personalized target problem assessment via Qualtrics or via video or phone call with a Research Assistant	After Venus survey completed
Focus Groups	Optional focus group to provide study team with feedback	After Venus survey completed
Earth Survey (Survey 4)	Full assessment (Table 4)	6 months post-intervention
Earth Survey (Survey 5)	Full assessment (Table 4)	12 months post intervention
ORCASTAIT Surveys	Cost, burden as described in ORCASTRAIT Protocol	Weekly, while in ORCASTRAIT

Phase 1

Measures. Aim 1: Feasibility will be assessed by measuring how many Care Partners who start the program successfully complete it. Care Partners will fill out our telehealth survey that asks them about acceptability.^(23, 24) Acceptability will also be assessed qualitatively using focus groups.⁽²⁵⁾ The focus groups will be conducted via videoconferencing and will be recorded and transcribed for analysis.^(15, 16)

Aim 2: Standard quantitative measures that were used in the earlier pilots^(15, 16) will be used to provide preliminary evidence for efficacy. The quantitative measures are grouped into 5 surveys: Mercury Baseline, Starlet, Venus, Earth (6 months post intervention) and Earth (12 months post intervention). Along with the ORCASTRAIT Living Lab suite of measures (demographics, activity, time with person with dementia, sleep-related behaviors), we assess burden using the RMBPC⁽²⁶⁾ and the 22-item Zarit Burden Interview (ZBI). To provide focus for the intervention, each Care Partner will identify and rate 2-3 specific target problems to address in STELLA. Pre-death grief will be assessed with the Marwit Meuser Caregiver Grief Index, Short Form (MMCGI-SF).⁽²⁷⁾ Care Partner plans for person with dementia placement will be assessed with the

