Aim 2: Efficacy will be assessed by calculating changes in the subjective scores before, during and after the intervention using linear regression models and controlling for age, sex and education. Since this is an exploratory (proof-of-concept) study with a small sample size, we do not expect statistically significant findings, but pre-post change and standard deviation of the change will be used to calculate the sample sizes for the next stage, a RCT (NIH Stage II⁽³²⁾, Phase 1) study.

Objective digital behavioral biomarker data collected from the ORCASTRAIT Living Lab (e.g., daily activity (steps), total sleep time, times together) will be assessed before, during and after the intervention and compared to subjective findings. Simple Spearman correlations will be used to explore the relationship of the objective continuous sensor-derived data to the subjective data, where the continuous objective digital data is collapsed to mean values which will serve as a point estimate prior to, during and after the intervention. We will compare the shift in the distribution of each of the digital behavioral biomarkers from baseline to identify relative changes during and after the intervention. We will compare the objective and subjective findings of the dyad to identify trends that correlate with burden (**Figure 1**)⁽³³⁾.

Aim 2 Anticipated Results and Implications. We anticipate that STELLA will reduce Care Partner burden and grief and improve family quality of life. These improvements in turn will decrease

Care Partner desire to place family members in long-term care. We expect these findings will be supported by both subjective and objective data.

Aim 3: Before Session 5, subjective and objective data (**Table 4**) will be compared to pre, mid- and post-intervention data to identify trends. Qualitative data will be gathered during the focus groups. Participants will be asked what they thought was most helpful about the intervention and what they thought of the format. The objective and subjective results will be used to identify which components of STELLA were most effective and which need to be modified to improve the potency of future iterations.

Aim 3 Anticipated Results and Implications. We expect to see an improvement in the objectives and subjective data, and we expect that we will need to revise the STELLA intervention. We will use information from the focus groups and the accrued data to revise as needed.

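### The next-stage RCT is to be sized from the pre-post change in treated Care Partners, which equals the between-arm difference only if untreated controls would not change, and nothing planned checks that

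*Combined protocol and SAP*

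**What the plan says.** The Analytic Plan (section 5, Phase 1, Aim 2) assesses efficacy through changes in the subjective scores before, during and after the intervention, "using linear regression models and controlling for age, sex and education". It calls the study exploratory, expects no statistically significant results, and gives the change scores one forward use: "pre-post change and standard deviation of the change will be used to calculate the sample sizes for the next stage, a RCT". No other input to that calculation is named.

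There is no control or waitlist group. Section 3 says "Care Partners will participate in an 8-week intervention in which a Guide" helps them with distressing symptoms, and section 4a sets the size: "Up to 40 Care Partners and their 40 care-recipients with ADRD will participate in this study". The digital biomarkers are likewise compared with participants' own baseline. The only planned comparison with people who do not take part is in Phase 2, Aim 2, and it concerns costs.

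The parent study is larger ("The ORCASTRAIT study (IRB#20236) is currently enrolling 120 dyads"), and Table 3 lists its weekly surveys of cost and burden. No planned analysis uses them to estimate change in the clinical scores without STELLA.

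**The concern.** A two-arm sample size needs a between-arm difference and an SD. The SD of change can supply the second. Since the plan names only the change and its SD, the mean change in treated Care Partners is left to serve as the first. That quantity includes any change that would have occurred anyway.

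The documents suggest two sources of such change, which pull in opposite directions.

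- **Apparent improvement.** Table 1 requires at least two RMBPC behaviours "that are bothersome to the Care Partner and occur 3 or more times/week at study enrollment", and the RMBPC is also an outcome. Selecting on a high value of an outcome invites regression to the mean. The pull may be weak, because the Background describes these symptoms as ones "that the majority of persons with dementia (PwD) experience". The argument applies to the RMBPC and is not shown for the other scales.
- **Hidden benefit.** Progression of dementia could worsen scores and mask an effect. This is more plausible at the 6- and 12-month Earth surveys than at the Venus survey, due "2 months after Session 1", which is the natural reading of the post-intervention point.

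At stake is the size of the next trial, which could be underpowered or larger than needed, without the team being able to tell which from this study.

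**Working it through.** **1. What can be reproduced.** The documents give no RCT sample size, mean change, SD, significance level or power. There is no figure of the plan's own to check, and the numbers below are illustrations under stated assumptions.

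**2. The identity.** In SD-of-change units, let δ be the true between-arm effect and b the mean change controls would show (positive means improvement). Then

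- treated pre-post change = δ + b
- between-arm difference = (δ + b) − b = δ

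The two agree only if b = 0. Regression on age, sex and education does not separate b from δ, because b is shared by all participants and there is no untreated group in the model.

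**3. Inputs assumed.** Two-sample t-test, two-sided level 0.05, 80% power, 1:1 allocation, equal SD of change in both arms, no dropout. True effects of 0.2, 0.3 and 0.4 SD; background change of ±0.05 and ±0.10 SD.

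**4. Method.** Size the RCT at δ + b, then evaluate its power at δ. As a normal approximation, n per arm = 2(1.96 + 0.84)²/d². For d = 0.3 this gives 15.7/0.09 ≈ 174; the exact t-test calculation gives 176. The t-test values used are: d = 0.10, 1571; 0.20, 394; 0.25, 253; 0.30, 176; 0.35, 130; 0.40, 100; 0.50, 64.

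**5. Results.**

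| True effect δ | Background b | Sized at δ + b | n per arm planned | n per arm needed | Planned / needed | Actual power |
|---|---|---|---|---|---|---|
| 0.3 | 0 | 0.30 | 176 | 176 | 1.00 | 80% |
| 0.3 | +0.05 | 0.35 | 130 | 176 | 0.74 | 67% |
| 0.3 | +0.10 | 0.40 | 100 | 176 | 0.57 | 56% |
| 0.3 | −0.05 | 0.25 | 253 | 176 | 1.44 | 92% |
| 0.3 | −0.10 | 0.20 | 394 | 176 | 2.24 | 99% |
| 0.2 | +0.10 | 0.30 | 176 | 394 | 0.45 | 46% |
| 0.2 | −0.10 | 0.10 | 1571 | 394 | 3.99 | >99% |
| 0.4 | +0.10 | 0.50 | 64 | 100 | 0.64 | 61% |
| 0.4 | −0.10 | 0.30 | 176 | 100 | 1.76 | 96% |

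**6. Tolerance.** The background improvement that lowers actual power to 70% is 0.026 SD for δ = 0.2, 0.038 for δ = 0.3 and 0.051 for δ = 0.4.

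**7. Second parameterisation.** Let controls change by a share f of the treated change. The required n is then multiplied by 1/(1 − f)². At f = 0.25 this is 1/0.5625 = 1.78, and power at the planned size falls from 80% to about 56%. At f = 0.5 it is 4, and power is about 29%. At f = −0.25 (controls worsen) it is 1/1.5625 = 0.64, so the planned trial is larger than needed.

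**8. Precision is a separate matter.** With the maximum of 40 Care Partners, the 95% CI half-width for the mean change is t(0.975, 39)/√40 = 2.023/6.325 = 0.32 SD of change. More treated participants would narrow this interval around δ + b, not around δ.

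**The case against.** The strongest reply is that the plan does not say the mean change will be entered unadjusted as the between-arm difference. A statistician could subtract an assumed control change first. That is true, but no such step appears in the text, and the change and its SD are the only inputs named. If the team intends a subtraction, the plan should say so and give the value.

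Second, this is an exploratory study, and harm occurs only if a later trial adopts the raw change without further justification. This limits the weight of the point: no result of the present study is put at risk. It does not remove the point, because sizing the RCT is the one use the plan gives these change scores beyond description.

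Third, the effects and background changes above are assumed. They show sensitivity, not a likely error, and no material bias is demonstrated at the Venus survey. This stands.

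Fourth, the remedy has limits of its own. Taking the SD of change from treated participants assumes that it carries over to controls and that the RCT is analysed on change scores. It is also imprecise: with 40 participants and normal data, the 95% CI for an SD runs from about 0.82 to 1.28 times the estimate, so the RCT size varies from about 0.67 to 1.65 times (0.82² and 1.28², before rounding). This is a reason to show the RCT size over that range. An alternative that keeps more of the authors' method is to state an assumed control change and show the RCT size over a range of values. That would also make the assumption visible, though it would still rest on a figure this study cannot supply.

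**Conclusion.** The concern holds. As written, the sizing rule gives a between-arm difference only if mean change in controls is zero. The documents do not state or defend that, and no planned analysis tests it. This rests on reading the named inputs as the whole calculation, which is the natural reading but not an explicit statement.

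The bias is of unknown sign and size and could be zero. For assumed true effects of 0.2 to 0.4 SD, a background improvement of 0.10 SD would leave the RCT with 46% to 61% power, and a background worsening of the same size would make it 1.8 to 4.0 times as large as needed. The problem is the use of the mean; the SD of change remains a reasonable input for a trial analysed on change scores. The sentence should be fixed, but the consequence falls on the next trial only.

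**What to change.** Replace the sentence on RCT sizing in the Analytic Plan, Phase 1, Aim 2 with:

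> Pre-post change will be reported descriptively with its 95% CI and will not be used as the RCT effect size. The RCT target will be a justified smallest meaningful between-arm difference for the chosen outcome and time point. This study will supply the SD of change with its 95% CI, and the RCT size will be shown over that range.

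Optionally, and as support only, compare change in burden with concurrent non-participants in the parent cohort. This requires that the parent protocol collects the same burden measure, which has to be checked. The comparison should be limited as far as possible to dyads who would meet the STELLA criteria, and self-selection should be acknowledged. It could give a non-randomised indication of direction, for burden only.

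The main change costs wording, with no extra participants or data. The team takes on the work of justifying a meaningful difference, and the projected RCT may turn out less favourable in size.

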Assessing Acceptability, Cost, and Efficacy of STELLA-Support via Technology: Living and Learning with Advancing AD

01/31/2022

NCT04335110

Protocol Title:

Assessing Acceptability, Cost, and Efficacy of STELLA-Support via Technology: Living and Learning with Advancing AD

Objectives

STELLA (Support via TTechnology: Living and Learning with Advancing Alzheimer's disease and related dementias) is a multicomponent video-conference based intervention designed to facilitate effective management of behavioral and psychological symptoms of dementia (BPSD). In the STELLA intervention, professionals ("Guides") meet with family members ("Care Partners") caring for persons with dementia. Working together, the Care Partners and Guides identify strategies to address upsetting behaviors in the moderate to late stages of dementia. The goal of this intervention is to reduce upsetting behaviors and thus care partner burden including costs.

The specific aims of this study are:

Phase 1

1. Using quantitative and qualitative approaches, assess feasibility and participant acceptability of (a) STELLA, and (b) the assessment methods (subjective measures and unobtrusive objective monitoring).
2. Using quantitative strategies, assess the preliminary effect of STELLA on (a) the affective impact of caregiving, Care Partner cognitive function and person with dementia quality of life, and on (b) Care Partner and person with dementia objective digital behavioral biomarkers (activity, sleep and time together).
3. Test the feasibility of employing digital behavioral biomarker data, combined with qualitative Care Partner feedback, to assess mechanisms of behavior change before, during and after the STELLA intervention.

Phase 2

1. Quantify the costs of delivering the STELLA intervention.
2. Quantify the cost efficacy of STELLA in relation to BPSD frequency and CP reactivity and assess the relationship between costs, BPSD, and care partner burden.

H1: There is a relationship between BPSD and cost: More BPSD behaviors and more CP reactivity to the BPSD are associated with higher out-of-pocket and implicit costs for families living with dementia.

H2: There is a relationship between out-of-pocket and implicit costs and objective measures of burden identified in the ORCASTRAIT Living Lab continuous home assessment. Higher objective burden will correlate with higher implicit and out-of-pocket costs.

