The STELLA Intervention. STELLA consists of 8 sessions: 4 sessions one-to-one, with the Care Partner and a Guide, and then 4 sessions with one Guide with up to four Care Partners (total small group will include as few as two and as many as 4 Care Partners) (**Table 2**). Each weekly session takes about 1 hour. The first four sessions allow for development of the Care Partner-Guide working relationship. In these sessions, the Care Partners identify behaviors (both the person with dementia's and the Care Partner's) which are upsetting to the family. Care Partners will be taught to use an "ABC" approach to identify activators of behaviors, the behaviors, and consequences of the behaviors. After they identify the ABCs, they will develop a plan to address the behavior and then test it. Based on Care Partner feedback from our pilots, we adapted the prototype intervention so that STELLA uses the ABC plan for both the person with dementia behaviors *and* Care Partner behaviors. After the four one-to-one sessions, Care Partners will meet in small groups with a Guide. Effective communication strategies, engagement in pleasant events, and coping will be addressed (**Table 2**). ⁽⁷⁾ The Guide will facilitate conversation and support between the Care Partners. Care Partners will be provided with each other's contact information. They will be encouraged to contact each other during and after the intervention. Due to schedule conflicts, there may be an up to two-week gap between Sessions 4 and 5.

Each Care Partner will have their own STELLA workbook to document their plans and progress (see "The STELLA Collaborative Handbook"). The booklet will be given or mailed to them prior to the first STELLA visit. They will have access to information on caring for person with dementia on the STELLA password-protected website which is under production. STELLA allows for some flexibility in scheduling if Care Partners have to re-schedule. Care Partners will be advised that the one hour sessions may be tiring and that they may end a session early if needed. In addition, Care Partners will need to find an activity for their care-recipients while they are engaged in the training session so they can focus on the material and protect their care-recipients' dignity. Some of the conversations will include discussions about challenging behaviors, which if overheard by the care recipient, may be upsetting.

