revised Desire to Institutionalize (DTI) scale.⁽²⁸⁾ Care Partner depression will be measured with the CESD-10⁽³⁰⁾ and role captivity will also be assessed.⁽³¹⁾ In addition to subjective assessments, we will evaluate the effect of STELLA on digital behavioral biomarkers (activity, time spent together and sleep) obtained from the ORCASTRAIT platform. Total daily activity, time together and alone, and sleep duration, will be assessed prior to, during, and after the intervention. Care Partners will complete all assessments electronically. A secure link to each assessment will be emailed to each CP. We will ask the CPs to complete the assessments within 5 days of receiving the email. If they do not, we will call them to assess their situation. If they do not complete surveys as outlined on the times listed in Table 3 they may not continue with the intervention.

Aim 3. To identify which components of STELLA are most helpful to Care Partners, we will assess the mechanisms of action for reducing burden, depression and grief and improving cognitive function and sleep. Care Partners will complete the surveys (**Table 3**) before the intervention, after Session 4 and after the intervention. An analysis of objective data (**Figure 1**) will also be done during the intervention. We will ask Care Partners in our focus groups to report what they found most helpful about STELLA.

Table 4: Subjective Assessment Descriptions

Measure	Description
Mercury Baseline	
Demographics	Demographics, including hours/week caregiving
Revised Memory & Behavioral Problems Checklist (RMBPC) ²³	Measure of frequency and reactivity to behavioral and psychological symptoms of dementia ²³
Personalized target problem assessment	Care partner-identified targeted problem assessment
Zarit Burden Interview (ZBI) ³³	4-item measure of burden
Center for Epidemiologic Studies Depression Scale (CESD-10) ³⁴	10-item depression measure
Marwit Meuser Caregiver Grief Index-Short Form (MMCGI-SF) ³⁵	Care partner pre-death grief ³⁵
Placement plan scale ³⁷	One-item assessment of plans for placement for family member with dementia ³⁷
QoL AD ³⁶	13-item assessment of quality of life for both the care partner and the person with dementia.
Starlet Survey	
ZBI ³³	
CESD-10 ³⁴	
Venus Survey	
RMBPC ²³	
 • See Baseline for descriptions • Baseline: 
 + STELLA contact survey + Experience Survey -Demographic survey
Personalized target problem assessment	

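### The Phase 1 Aim 3 analysis says the results will show which STELLA components were most effective, but one fixed sequence with no Phase 1 comparator cannot separate components from time, order and format

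*Combined protocol and SAP*

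**What the plan says.** The document words Phase 1 Aim 3 in three ways.

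- **Objectives, Phase 1, aim 3:** a feasibility aim. "Test the feasibility of employing digital behavioral biomarker data, combined with qualitative Care Partner feedback, to assess mechanisms of behavior change".
- **Section 5, Measures, Aim 3:** the purpose is to find the components most helpful to Care Partners, and "we will assess the mechanisms of action for reducing burden, depression and grief and improving cognitive function and sleep". Surveys are taken "before the intervention, after Session 4 and after the intervention".
- **Section 5, Analytic Plan, Phase 1, Aim 3:** the strongest wording. "The objective and subjective results will be used to identify which components of STELLA were most effective and which need to be modified". The stated purpose is to strengthen later versions of STELLA.

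On delivery, section 5 says "STELLA consists of 8 sessions: 4 sessions one-to-one, with the Care Partner and a Guide", followed by four small-group sessions. Table 2 assigns one topic to each week. Section 4 gives the size: "Up to 40 Care Partners and their 40 care-recipients with ADRD will participate in this study". No component is omitted, re-ordered or randomised, and Phase 1 describes no comparison group.

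On measurement, Table 3 describes the mid-point Starlet survey as "Electronic assessment of depression, burden", due "1 month after Session 1". Table 4 agrees: it holds only the ZBI and the CESD-10. Table 3 also lists Earth surveys 6 and 12 months after the intervention and a weekly ORCASTRAIT survey of cost and burden. Sensors record activity, time together and sleep before, during and after the intervention.

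**The concern.** Saying which component was most effective is a causal comparison between parts of the package. It needs some Care Partners to receive a part at a time when others do not, or a defensible assumption about what would have happened anyway. The plan has neither.

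Regression to the mean makes this concrete. Table 1 admits dyads only if at least two bothersome behaviors occur three or more times a week at enrollment. Some early improvement is then to be expected without any effect, and it would be credited to Sessions 1-4. A delayed benefit of the one-to-one sessions would be credited to the group sessions in the same way.

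At stake is the revision of STELLA before the planned RCT. Components could be kept, changed or dropped partly on a time pattern that cannot bear that reading.

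**Working it through.** The plan gives no calculation for Aim 3, so there is no figure to reproduce. The question is whether component effects can be estimated from the planned data, whatever the sample size.

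**Model.** Let the mean outcome at time t be μ + π(t) + the sum of β(k) over all components k delivered by t. Here π(t) is the time effect, with π = 0 at baseline, and β(k) is the effect of component k. An effect is estimable only if it is a combination of the observed means, which a rank check of the design matrix shows.

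**1. Two blocks, three surveys (before, mid-point, after).**
- First change = π1 + β1.
- Second change = (π2 − π1) + β2.
- Difference between the changes = (β1 − β2) + (2π1 − π2).

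The matrix, with columns intercept, π1, π2, β1, β2, has rows (1,0,0,0,0), (1,1,0,1,0) and (1,0,1,1,1). Its rank is 3 for 5 unknowns. Neither β1 nor β1 − β2 is estimable. The contrast is recovered only if 2π1 = π2, that is, if the underlying trend is equal in the two intervals, and if nothing carries over from the first block. Regression to the mean acts mostly early, so it breaks the first condition.

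**2. Eight topics, three surveys, assuming no time trend at all.** The unknowns are one intercept and eight topic effects. The rank is 3 of 9, and no topic effect is estimable. Adding the 6- and 12-month surveys leaves the rank at 3, because exposure no longer changes after Session 8.

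**3. Weekly data: baseline plus eight weeks (sensors or the parent-study survey).**

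| Time effects allowed | Rank | Result |
|---|---|---|
| One per week | 9 of 17 | No topic effect, and no contrast between topics, is estimable |
| Linear trend only | 9 of 10 | No topic effect is estimable; topics are fixed only up to a common constant |
| None | 9 of 9 | All eight are estimable |

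The last row requires no time trend and each topic to act in full in its own week, without delay. In the middle row topics could be ranked, but only if the trend is exactly equal every week and effects are immediate. The only stated summary of the sensor data, under Aim 2, reduces them to one mean each for before, during and after, which discards the weekly detail.

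**4. Format.** One-to-one is always Sessions 1-4 and group is always Sessions 5-8. Format therefore coincides with both topic set and time.

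**5. Mid-point (secondary).** Starlet has burden and depression only. Grief is among the outcomes named for Aim 3, but the MMCGI-SF is not in Starlet, nor is the RMBPC. Within the intervention window each has one change (before to after), not two. Timing is also loose. With weekly sessions, Session 5 falls on day 7 × 4 = 28, while one month after Session 1 is day 28 to 31, and Care Partners are asked to respond within 5 days. Unless the optional break of up to two weeks is used, Starlet may not precede Session 5.

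**The case against.** The strongest reply is that this is formative work. The study is declared a proof of concept that expects no significant findings and leads to an RCT. The component sentence aims at improving later versions, and revision is to use focus groups as well as accrued data. Focus groups ask directly what helped most and what Care Partners thought of the format. Sensors and the weekly survey also supply far more data during the intervention than Starlet does.

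Much of this stands, and it limits the point.

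- A reader might infer that outcomes are measured only before, at one month and at two months, so that grief and the RMBPC have a single contrast overall. The document does not support this. Both are repeated at 6 and 12 months, and the single change applies only within the intervention window.
- A reader might infer that the short Starlet survey is the cause. It is not. A longer mid-point survey would leave topic, format and time confounded.
- A reader might infer that Aim 3 as a whole fails, or that revision rests on the time pattern alone. The feasibility aim in the Objectives is within reach, and participant report is a planned input.

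What does not stand is the appeal to exploratory status. That caveat sits under Aim 2 and concerns significance in a small sample, whereas confounding does not shrink with size. Focus groups are optional and measure perceived helpfulness, not effectiveness. Missed sessions create some variation in exposure, but it is self-selected and no analysis of it is planned. The Phase 2 comparison with non-participants concerns costs and does not vary components.

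**Conclusion.** The concern holds for the sentence in the Analytic Plan. Under one fixed sequence with no Phase 1 comparator, the quantitative results cannot identify which component was most effective. With free time effects, the data give 3 independent quantities for 5 unknowns (two blocks, surveys) or 9 for 17 (eight topics, weekly data). Eight topics cannot be separated from the surveys even with no time trend (3 of 9).

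The conclusion is conditional in one respect. Weekly data would yield the topic effects if there were no time trend and each topic acted at once. Nothing in the document supports those assumptions, and the entry criterion argues against the first. The missing mid-point values for grief and the RMBPC are a lesser, separate limit on description.

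The change is worth making because it is cheap and the sentence feeds a decision, but no efficacy conclusion rests on it.

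**What to change.** 1. Reword the Aim 3 sentence in the Analytic Plan to agree with the Objectives. For example: survey and digital biomarker data will describe change before, during and after the intervention, by half where measured, and will not be used to say which component was most effective. Keep the biomarkers in this description; it should not be limited to burden and depression.
2. State that decisions on components rest on perceived helpfulness, from the planned focus groups plus one rating per session topic (up to 8 items) in the Venus Experience Survey. Table 4 describes that survey as 16 items plus comments on satisfaction, privacy and ease of use, and the items are not shown. If they already cover each topic, no addition is needed.
3. State that grief and the RMBPC have no value at the middle of the intervention. Adding them to Starlet would allow description by half at the price of a longer survey, but should not be presented as a remedy for the confounding.

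The cost is a weaker claim, a few sentences and at most eight short items in an existing survey.
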